Appendix B. Weight-Based SC Insulin Dosing -NPO, Liquid Diet Only, or Minimal Diet Intake

- Age \geq 70 years, eGFR <60mL/min, underweight, risk for hypoglycemia
 - Total Daily Insulin Dose = 0.1 units/kg (100% Basal Glargine)
 - Correctional Regular insulin (every 6 hours) or aspart (every 4 hours) = Low (1 unit:50 mg/dL BG >150 mg/dL)
- Normal Body Weight (BMI 18.5-25)
 - Total Daily Insulin Dose = 0.2 units/kg (100% Basal Glargine)
 - Correctional Regular insulin (every 6 hours) or aspart (every 4 hours) = Low (1 unit:50 mg/dL BG >150 mg/dL)
- Overweight (BMI 25-30)
 - Total Daily Insulin Dose = 0.25 units/kg (100% Basal Glargine)
 - Correctional Regular insulin (every 6 hours) or aspart (every 4 hours) = Medium (2 units:50 mg/dL BG >150 mg/dL)
- Obese (BMI >30)
 - Total Daily Insulin Dose = 0.3 units/kg (100% Basal Glargine)
 - Correctional Regular insulin (every 6 hours) or aspart (every 4 hours) = Medium (2 units:50 mg/dL BG >150 mg/dL)

Additional Considerations:

- Dextrose containing maintenance IV fluids are recommended for patients with prolonged NPO status receiving scheduled insulin.
- If blood glucose is less than 100 mg/dl, nurse to hold basal insulin and notify physician.

Appendix C. Management of SC Insulin Dosing –Continuous tube feedings or PN

- Age > 70 years, eGFR <60mL/min, underweight, risk for hypoglycemia
 - Total Daily Insulin Dose = 0.2 units/kg
 - 0.1 units/kg/day basal glargine
 - 0.025 units/kg every 6 hours nutritional regular insulin
 - Correctional Regular insulin every 6 hours = Low (1 unit:50 mg/dL BG >150 mg/dL)
- Normal Body Weight (BMI 18.5-25)
 - Total Daily Insulin Dose = 0.4 units/kg
 - 0.2 units/kg/day basal glargine
 - 0.05 units/kg every 6 hours nutritional regular insulin
 - Correctional Regular insulin every 6 hours = Low (1 unit:50 mg/dL BG >150 mg/dL)
- Overweight or Obese (BMI >25)
 - Total Daily Insulin Dose = 0.5 units/kg
 - 0.25 units/kg/day basal glargine
 - 0.06 units/kg every 6 hours nutritional regular insulin
 - Correctional Regular insulin every 6 hours = Medium (2 units:50 mg/dL BG >150 mg/dL)

Additional Considerations:

- If patient is receiving bolus enteral tube feedings, daily nutritional insulin dose should be evenly divided and given prior to each feeding.
- For cyclic enteral tube feeding or parenteral nutrition (e.g. nocturnal only), insulin dosing must be individualized and coincide with nutritional regimen.
- Correctional regular insulin is given in addition to nutritional regular insulin dose.
- If blood glucose is less than 100 mg/dl, nurse to hold nutritional/basal insulin and notify physician.
- If nutrition is interrupted: nurse to notify physician, start dextrose 5%/0.45% NaCl infusion at twice the rate of nutrition order, hold scheduled regular insulin, give glargine and correctional regular insulin.

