Appendix A. Weight-Based SC Insulin Dosing – PO diet eating full meals

- Age > 70 years, eGFR <60mL/min, underweight, risk for hypoglycemia
 - Total Daily Insulin Dose = 0.2 units/kg
 - 0.1 unit/kg/day basal glargine
 - 0.03-0.05 units/kg/meal nutritional aspart
 - Correctional Aspart AC = Low (1 unit:50 mg/dL BG >150 mg/dL)
- Normal Body Weight (BMI 18.5-25)
 - Total Daily Insulin Dose = 0.4 units/kg
 - 0.2 unit/kg/day basal glargine
 - 0.07 units/kg/meal nutritional aspart
 - Correctional Aspart AC = Low (1 unit:50 mg/dL BG >150 mg/dL)
- Overweight or Obese (BMI >25)
 - Total Daily Insulin Dose = 0.5 units/kg
 - 0.25 unit/kg/day basal glargine
 - 0.08 units/kg/meal nutritional aspart
 - Correctional Aspart AC = Medium (2 units:50 mg/dL BG >150 mg/dL)

Additional Considerations:

- Aspart dose should be given immediately prior to meal. If it is unknown if patient will eat, hold aspart prior to meal and give after meal if patient consumes at least 50%. Give aspart dose within 15 minutes of first bite.
- If patient is expected not to eat or consumes less than 50% of meal: nurse to notify physician, hold scheduled nutritional aspart dose, continue basal glargine, and give aspart correctional sliding scale.
- Correctional aspart to be given in addition to nutritional aspart dose.
- If blood glucose is less than 100 mg/dl, nurse to hold nutritional/correctional insulin and notify physician. Basal insulin should be continued as prescribed unless instructed otherwise by physician orders.
- If patient has abrupt change in diet (e.g. made NPO for urgent procedure), nurse to notify physician. It is recommended to start dextrose containing IV fluids and continue basal insulin glargine to prevent rebound hyperglycemia. Insulin regimen should be re-evaluated by provider as warranted.
- Pre-meal blood glucose goal is 100-150 mg/dl.

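### Appendix C gives opposite instructions for glargine when nutrition is interrupted while glucose is below 100 mg/dL, and states no order of priority

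*Combined protocol and SAP*

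**What the plan says.** The Additional Considerations in Appendix C contain two consecutive nurse-level rules.

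- Low glucose: "If blood glucose is less than 100 mg/dl, nurse to hold nutritional/basal insulin and notify physician".
- Interrupted nutrition: "If nutrition is interrupted: nurse to notify physician, start dextrose 5%/0.45% NaCl infusion at twice the rate of nutrition order", followed by "hold scheduled regular insulin, give glargine and correctional regular insulin".

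The scheduled basal doses in Appendix C are "0.1 units/kg/day basal glargine" for the older or higher-risk group, "0.2 units/kg/day basal glargine" for normal weight and "0.25 units/kg/day basal glargine" for overweight or obese patients. No other basal insulin is listed there.

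Two neighbouring appendices bear on the secondary note. Appendix A (patients eating full meals) keeps basal insulin going below 100 mg/dL unless a physician orders otherwise. For an abrupt change of diet, such as being made NPO, it says: "It is recommended to start dextrose containing IV fluids and continue basal insulin glargine to prevent rebound hyperglycemia". It also asks the provider to re-evaluate the regimen as needed. Appendix B (NPO, liquid diet or minimal intake) says: "If blood glucose is less than 100 mg/dl, nurse to hold basal insulin and notify physician".

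Section 5.i (Inpatient Hyperglycemia Management) leaves subcutaneous regimens to the treating ICU team and presents the appendices as recommended dosing. It recommends the subcutaneous route only for haemodynamically stable patients with consistent nutrition.

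**The concern.** The two Appendix C bullets have different triggers, a glucose value and a feeding event, and nothing prevents both from being true at once. The low-glucose bullet has no exception for stopped feeding, and the interruption bullet has no glucose condition. A nurse who follows the page literally cannot comply with both.

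The first thing at stake is patient safety: whether a long-acting insulin dose is given or held at a time when nutrition has stopped and glucose is already below 100 mg/dL. The second is consistency of care. Section 5.e says that care does not differ for participants except in the method of glucose monitoring, and the primary outcome is time with glucose at 70-180 mg/dL. A dosing instruction that can be read in two ways adds avoidable variation in how patients are managed.

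**Working it through.** The plan has no figure of its own on this point, so the check sets the rules side by side and then applies simple arithmetic to the stated doses.

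**Step 1. The two Appendix C bullets, by type of insulin, when both triggers hold.**

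| Insulin | Glucose below 100 mg/dL | Nutrition interrupted | Agree? |
|---|---|---|---|
| Scheduled (nutritional) regular | hold | hold | yes |
| Glargine (basal) | hold | give | **no** |
| Correctional regular | not mentioned | give | no dose arises: the scale starts above 150 mg/dL |

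The conflict is therefore confined to glargine. No sentence in Appendix C, or in sections 5.i and 5.j on hyperglycemia and hypoglycemia management, ranks one bullet above the other.

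**Step 2. When it has a consequence.** Glargine is written as a daily dose. Three things must coincide: nutrition is interrupted, glucose is below 100 mg/dL, and a glargine dose is due.

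**Step 3. Size of the disputed dose.** Inputs are the Appendix C basal and total daily doses. Body weight is not in the documents, so 80 kg is assumed, with a range of 60 to 100 kg. Dose = weight × basal units/kg/day.

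| Appendix C group | Basal (units/kg/day) | 80 kg (units/day) | 60 to 100 kg (units/day) | Share of total daily dose |
|---|---|---|---|---|
| Older or higher risk | 0.1 | 80 × 0.1 = 8 | 6 to 10 | 0.1/0.2 = 50% |
| Normal weight | 0.2 | 80 × 0.2 = 16 | 12 to 20 | 0.2/0.4 = 50% |
| Overweight or obese | 0.25 | 80 × 0.25 = 20 | 15 to 25 | 0.25/0.5 = 50% |

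Under the low-glucose bullet the corresponding figure is 0 while the hold lasts. The right-hand figures assume that giving glargine means the scheduled dose. The bullet states neither a dose nor a reduction.

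**Step 4. Appendix A against Appendix B below 100 mg/dL.** Appendix A continues basal insulin, subject to physician orders, and Appendix B holds it. Each is coherent for its own diet state. What is missing is the point at which a patient on meals who is made NPO stops being managed under A and starts under B. Until that is stated, either page could be consulted for the same patient.

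**Step 5. What cannot be computed.** The documents give no rate for the joint event and no relation between a held or given dose and time in range. No effect on an outcome can be derived. The sample-size calculation does not use any of these rules.

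**The case against.** The strongest reply is that the appendices are advisory. Section 5.i leaves the subcutaneous regimen to the ICU team, prefers intravenous infusion when nutrition is inconsistent or the patient is NPO, and recommends the subcutaneous route only for stable patients with consistent nutrition. Both Appendix C bullets have the physician notified, so holding could mean holding until an order arrives and not forfeiting the day's dose. The interruption bullet also starts dextrose and holds scheduled regular insulin. All of this stands. It narrows exposure and gives a route to resolution, but it does not remove the conflict, because each bullet tells the nurse to act as well as to notify. Appendix C also writes a rule for interruption, so its authors foresaw it.

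Three stronger readings are tempting, and the documents do not support them.

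- *Appendices A and B contradict each other in the same way.* They cover different diet states. Appendix A only recommends continuing glargine, lets physician orders override, and calls for re-evaluation. This is an unclear handover.
- *The two triggers are likely to coincide, and the result shifts time in range.* No passage gives a frequency or an effect, and the likelihood argument overlooks the dextrose step.
- *The conflict acts differently by arm, because CGM staff see more readings.* The pre-set CGM alerts are at 70, 55 and 250 mg/dL, with none at 100. More action on more readings would in any case be part of the monitoring strategies being compared.

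**Conclusion.** The point holds as an internal contradiction in Appendix C. A tube-fed or parenterally fed patient on subcutaneous insulin whose nutrition is interrupted, whose glucose is below 100 mg/dL and whose glargine is due has opposite instructions for that drug. The disputed amount is 0 against 0.1, 0.2 or 0.25 units/kg/day, half the stated total daily dose in each group. This rests on reading the interruption bullet as meaning the scheduled dose. The unit figures rest in addition on an assumed weight.

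Confidence is high for the wording conflict. No claim is made about how often it occurs, its effect on any outcome, or a difference between arms. The Appendix A to B handover is a secondary gap in the same area. Neither point touches the primary analysis or the sample size, but a contradiction in insulin instructions is worth correcting on safety grounds alone.

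**What to change.** Reconcile the two Appendix C bullets by stating which one governs glargine when nutrition is interrupted and glucose is below 100 mg/dL. State also when a patient on meals who is made NPO passes from Appendix A to Appendix B, so that it is clear which basal rule applies below 100 mg/dL. Which rule should prevail is a clinical decision for the sponsor's clinicians, and none is proposed here. A separate statement that the rule is the same in both arms is not essential, since section 5.e already confines the difference in care to the monitoring method.

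The cost is one or two sentences in the appendices, a minor amendment and a short re-briefing of nursing staff. No additional patients, procedures or data are needed.

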Appendix D. Management of Intravenous Insulin Infusion

Excel tool (pictured below) developed using the algorithm of the paper-based IIP developed by the University of Pittsburgh Medical Center (UPMC).

- Initial IV insulin infusion rate based on initial BG level
- Adjusted IV insulin infusion rate based on current BG, change in BG from previous, and current IV insulin infusion rate
- Instructions for converting from IV insulin infusion to SC insulin are provided, based on the average hourly rate of IV insulin

Initial Infusion Rate Calculator, Initial Infusion Rate Adjustment Calculator, Instructions for Converting from Intravenous to Subcutaneous Infusion

Initial insulin infusion rate calculator				
Initial blood glucose (mg/dL)				
Initial insulin infusion rate/instructions				
Insulin infusion rate	adjustment calculator			
Instructions: 1. Input current insulin infusion rate, current blood glucose, a change in blood glucose is accurate (blue box).	nd last blood glucose (i.e. the previous 1-2 hours) into the green boxes; verify the			
Adjust the patient's insulin infusion to the new rate (yellow to re-check blood glucose.	box) and follow the instructions in the red box for addition al orders and for when			
Note: This calculator should be used for adjustments in rate of	only; if the drip was held temporarily per instructions, follow those instructions			
Current insulin infusion rate (units/hr)				
Current blood glucose (mg/dL)				
Previous blood glucose (mg/dL)				
(
Change in blood glucose (mg/dL)	0			
New insulin infusion rate (units/hr)				
Additional instructions				
Instructions for conver	ting from IV to subcutaneous insulin			
1. Determine the AVERAGE hourly rate of IV insulin (over the past 5-8 hours) and multiply by 24 hours to determine the daily IV insulin requirement.				
 Multiply by the daily IV insulin requirement by 2/3 - this will be the daily amount of subcutaneous insulin to be given to the patient. a. Give 50% of the daily subcutaneous insulin as LONG acting (e.g. insulin NPH, glargine). b. Give 50% of the daily subcutaneous insulin as SHORT/RAPID acting (e.g. insulin R, aspart) in divided doses. 				
3. Order correctional insulin to cover for hyperglycemia.				

Figure 1: The nurse obtains a point-of-care blood glucose and manually enters the value into the tool. The tool then calculates the new insulin infusion rate and provides any additional instructions.

NOTE: Patients without a history of insulin-dependent diabetes who are receiving LESS THAN 2 units/hr of IV insulin may not require transition to scheduled subcutaneous insulin (i.e. they may not require insulin after stopping the infusion).

Protocol IRB version 03.09.04 PI version 10/0/2022

IV Insulin Infusion Titration

BG (mg/dL)	Current rate 0.1-3.9 units/hour	Current rate 4-6.9 units/hour	Current rate 7-10 units/hour	Current rate >10 units/hour*	
<70	(1) D/C insulin. Give 50mL (1 amp) D50 IV. Recheck BG in 15 min. Repeat as necessary. (Do not restart insulin until at least 1 hr after D50.) Notify MD. If no continuous glucose, start IV fluid as per page 1. Restart insulin at 50% (half) previous rate when BG >140 AND it is at least 1 hr after D50. Recheck BG in 1 hr.				
70-99	(2) D/C insulin. Recheck BG in 1 hr and then hourly. When BG >140, restart insulin but decrease rate by 50% (half) and recheck BG in 1 hr.				
100-139	(3.1) If BG drop >25 mg/dl from last check, D/C insulin. Recheck BG in1 hr and then hourly. When BG >140, restart insulin but decrease rate by 50% (half) and recheck BG in 1 hr.	(4.1) If BG drop >25 mg/dl from last check, D/C insulin. Recheck BG in 1 hr and then hourly. When BG >140, restart insulin but decrease rate by 2 units/hr and recheck BG in 1 hr.	(5.1) If BG drop >25 mg/dl from last check, D/C insulin. Recheck BG in 1 hr and then hourly. When BG >140, restart insulin but decrease rate by 3 units/hr and recheck BG in 1 hr.	(6.1) If BG drop >25 mg/dl from last check, D/C insulin. Recheck BG in 1 hr and then hourly. When BG >140, restart insulin but decrease rate by 4 units/hr and recheck BG in 1 hr.	
	(3.2) Otherwise, decrease by 0.5 units/hr (if current rate <0.5 units/hr, then D/C) and recheck BG in 1 hr.	(4.2) Otherwise, decrease rate by 1 unit and recheck BG in 1 hr.	(5.2) Otherwise, decrease rate by 1.5 units and recheck BG in 1 hr.	(6.2) Otherwise, decrease rate by 2 units and recheck BG in 1 hr.	
140-180	(7.1) If BG drop >50 mg/dl from last check, D/C insulin . Recheck BG in 1 hr and then hourly. Restart insulin (as long as BG>140), but decrease rate by 50% (half) and recheck BG in 1 hr.	(8.1) If BG drop >50 mg/dl from last check, D/C insulin. Recheck BG in 1 hr and then hourly. Restart insulin (as long as BG>140), but decrease rate by 2 units/hr and recheck BG in 1 hr.	(9.1) If BG drop >50 mg/dl from last check, D/C insulin. Recheck BG in 1 hr and then hourly. Restart insulin (as long as BG>140), but decrease rate by 3 units/hr and recheck BG in 1 hr.	(10.1) If BG drop >50 mg/dl from last check, D/C insulin. Recheck BG in 1 hr and then hourly. Restart insulin (as long as BG>140), but decrease rate by 4 units/hr and recheck BG in 1 hr.	
	(7.2) If BG drop 25-50 mg/dl from last check, decrease rate by 50% (half) and recheck BG in 1 hr.	(8.2) If BG drop 25-50 mg/dl from last check, decrease by 2 units/hr and recheck BG in 1 hr	(9.2) If BG drop 25-50 mg/dl from last check, decrease by 3 units/hr and recheck BG in 1 hr	(10.2) If BG drop 25-50 mg/dl from last check, decrease by 4 units/hr and recheck BG in 1 hr	
	(7.3) Otherwise, make no changes. If BGs 140-180 for 2 consecutive hours, recheck q2h.	(8.3) Otherwise, make no changes. If BGs 140-180 for 2 consecutive hours, recheck q2h.	(9.3) Otherwise, make no changes. If BGs 140-180 for 2 consecutive hours, recheck q2h.	(10.3) Otherwise, make no changes. If BGs 140-180 for 2 consecutive hours, recheck q2h.	
181-250	(11.1) If BG drop >50 mg/dl, decrease rate by 50% (half) and recheck BG in 1 hr.	(12.1) If BG drop >50 mg/dl, decrease rate by 2 units/hr and recheck BG in 1 hr	(13.1) If BG drop >50 mg/dl, decrease rate by 3 units/hr and recheck BG in 1 hr	(14.1) If BG drop >50 mg/dl, decrease rate by 4 units/hr and recheck BG in 1 hr	
	(11.2) If BG drop 25-50 mg/dl from last check, make no change and recheck BG in 1 hr	(12.2) If BG drop 25-50 mg/dl from last check, make no change and recheck BG in 1 hr	(13.2) If BG drop 25-50 mg/dl from last check, make no change and recheck BG in 1 hr	(14.2) If BG drop 25-50 mg/dl from last check, make no change and recheck BG in 1 hr	
	(11.3) Otherwise, increase rate by 1 unit/hr and recheck BG in 1 hr.	(12.3) Otherwise, increase rate by 1.5 units/hr and recheck BG in 1 hr.	(13.3) Otherwise, increase rate by 2 units/hr and recheck BG in 1 hr.	(14.3) Otherwise, increase rate by 3 units/hr and recheck BG in 1 hr.	
>250	(15.1) If BG drop > 25 mg/dl from last check, make no change and recheck BG in 1 hr	(16.1) If BG drop ≥25 mg/dl from last check, make no change and recheck BG in 1 hr	(17.1) If BG drop > 25 mg/dl from last check, make no change and recheck BG in 1 hr	(18.1) If BG drop ≥25 mg/dl from last check, make no change and recheck BG in 1 hr	
	(15.2) Otherwise, give 2 units insulin IV push AND increase rate by 1 unit/hr. Recheck BG in 1 hr.*	(16.2) Otherwise, give 2 units insulin IV push AND increase rate by 1.5 units/hr. Recheck BG in 1 hr.*	(17.2) Otherwise, give 2 units insulin IV push AND increase rate by 2 units/hr. Recheck BG in 1 hr.*	(18.2) Otherwise, give 2 units insulin IV push AND increase rate by 3 units/hr. Recheck BG in 1 hr.*	

*Notify MD when insulin infusion rate exceeds 10 units/hr or if 4 consecutive BGs are >250 mg/dL.

Reference:

University of Pittsburgh Medical Center. Regular Insulin IV Infusion Protocol: Goal Blood Glucose 140–180 mg/dL. (Updated: Nov 30, 2009.) 2009. http://inpatient.aace.com/sites/all/files/UPMC_140-180_IV_Insulin_Protocol.pdf.

Appendix E. CGM Blood Glucose Target Ranges, defined in CGM interpretation guidelines:

- DM type 1/type 2
 - Time in Range (TIR)
 - BG 70-180 mg/dL
 - >70% of readings; >16 h, 48 min per day
 - Time Below Range (TBR)
 - BG <70 mg/dL
 - <4% of readings; <1 h per day
 - BG <54 mg/dL
 - <1% of readings; <15 min per day
 - Time Above Range (TAR)
 - BG >180 mg/dL
 - <25% of readings; <6 h per day
 - BG >250 mg/dL
 - <5% of readings; <1 h, 12 min per day
- Older/high-risk DM type 1/type 2
 - Time in Range (TIR)

- BG 70-180 mg/dL
 - >50% of readings; >12 h per day
- Time Below Range (TBR)
 - BG <70 mg/dL
 - <1% of readings; <15 min per day
- Time Above Range (TAR)
 - BG >250 mg/dL
 - <10% of readings; < 2h, 24 min per day
